### 5.3.4.4 Efficacy Laboratory Summary Figures

The Mean result  $\pm$  SE will be presented by cohort (Cohort 1 wAIHA / Cohort 2 CAD) for each of the laboratory parameters for the ITT Set and Per Protocol Set as the following:

- Part A + B Lab Results:
  - Lab results at all scheduled visits through Part A Visit 15 and from Part B Baseline through end of study
  - Change from Part A + B Baseline lab result at all post-baseline visits through Part A Visit 15 and from Part B Baseline through end of study

Version 1.0

### • **Part B Lab Results**:

Change from Part B Baseline lab results at all post-baseline visits

#### 5.3.5 Pharmacodynamics

#### 5.3.5.1 Parameters

PD parameters include the following:

- 1. Complement CH50
- 2. Complement AH50
- 3. Complement C3

Additional PD parameters also include the following:

- C3 deposition on RBCs
  - Percent Type I
  - Percent Type II
  - Percent Type III
  - Percent Type I+II
  - Percent C3d on RBC

where:

$$%C3d on (Type I + II RBCs) = \frac{\binom{Events (C3d (CD59 HighType1 norm RBC) +}{Events (C3d (CD59 dim Type II RBC)})}{\binom{Events CD59 high Type 1 norm (RBC) +}{Events CD59 dim Type II (RBC)}} x 100$$

and where:

% C3d on RBC = 
$$\frac{C3d + Gly RBC Events}{Gly + RBC Events} \times 100$$

Study Day 1 will be considered the Part A+ B Baseline for the PD assessments. If this is missing, the screening assessment, if available, will be used as Part A + B Baseline. Part B Baseline will be considered as the last assessment before the first 1080mg APL-2 dose for each subject.
#### 5.3.5.2 PD Listings

The following listings will be prepared for the PD Set:

- PD Results and Change from Baseline will be presented in separate listings which will include:
  - $\circ \quad \underline{Part A + B}:$ 
    - PD Results at all Part A + B visits with Change from Part A + B Baseline and Percent Change from Part A + B Baseline
  - Part B:
    - PD Results at all Part B visits with Change from Part B Baseline and Percent Change from Part B Baseline

#### 5.3.5.3 PD Summary Tables

- The following summary statistics will be presented for each of the PD parameters by Cohort (Cohort 1 wAIHA / Cohort 2 CAD) for the PD Set and Per Protocol Set for the following:
- Part A + B PD Results:
  - Lab results at all scheduled visits through Part A Visit 15 and from Part B Baseline through end of study
  - Change from Part A + B Baseline lab result at all post-baseline visits through Part A Visit 15 and from Part B Baseline through end of study
  - Percent Change from Part A + B Baseline lab result at all postbaseline visits through Part A Visit 15 and from Part B Baseline through end of study
- Part B PD Results:
  - o Lab results at Part B Baseline and all scheduled Part B visits

Apellis Pharmaceuticals, Inc.
Protocol: APL2-CP-AIHA-208
Part B Long Term Extension Statistical Analysis Plan

- Change from Part B Baseline lab result at all post-baseline visits
- Percent Change from Part B Baseline lab result at all postbaseline visits

# 5.3.5.4 PD Summary Figures

The following figures mean result ± SE will be presented by cohort (Cohort 1 wAIHA / Cohort 2 CAD) for each of the PD parameters (CH50, AH50, Complement C3, C3d Type I, C3d Type II, C3d Type I+II, and C3d on RBC) for the PD Set and Per Protocol Set:

# • Part A + B PD Results:

- Lab results at all scheduled visits through Part A Visit 15 and from Part B Baseline through end of study
- Change from Part A + B Baseline lab result at all post-baseline visits through Part A Visit 15 and from Part B Baseline through end of study

# • Part B PD Results:

Change from Part B Baseline lab results at all post-baseline visits

# 5.3.6 Anti-drug antibody Assay

This data will be presented in listings.

# 5.4 Pharmacokinetic Analysis

All summaries and analyses of the pharmacokinetic data will be based on the Pharmacokinetic Set.

# 5.4.1 Pharmacokinetic Concentration Summaries

APL-2 concentrations reported as below the limit of quantification (BLQ) will be taken as zero for linear plots, and equal to the lower limit of quantification (LLOQ) for semi-logarithmic plots. For the computation of descriptive statistics, BLQ will be taken as zero, except for the calculation of the geometric mean where the LLOQ will be used.

Version 1.0

A listing of all APL-2 concentrations will be presented by dose. The actual study time will be listed, along with the deviation and percent deviation from nominal time.

For Part A, APL-2 concentrations will be summarized by planned study visit windows using descriptive statistics by randomized dose group, actual dose at the time of the visit. That is, at each visit, the descriptive statistics will be presented for:

- All randomized 270mg dose group, regardless of current dose
- All randomized 360mg dose group, regardless of current dose
- Subjects randomized to 270mg and on 270mg dose at time of visit
- Subjects randomized to 360mg and on 360mg dose at time of visit

For Part B, APL-2 concentrations will be summarized by planned study visit windows using descriptive statistics by cohort. The number of subjects with a value > BLQ will also be tabulated.

If a subject discontinues APL-2 dosing, then concentrations from samples collected more than 1 day after the last dose will be excluded from calculations.

For Part A, Linear and log-linear ( $\pm$  SE) concentration profile plots against time will be produced for each dose group.

For Part B, Linear and log-linear ( $\pm$  SE) concentration profile plots against time will be produced for each cohort.

For all time on-study, individual plots will be presented for PK concentration by study day. The individual plots will include an overlay of APL-2 dosing, also aligned by study day.

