# 12.4 Treatment Period (Day 1 to Day 336)

Subjects will receive daily SC doses of APL-2 on Days 1 through Day 336. APL-2 will be administered at the clinical site by study personnel or off-site at the subject's home, workplace, or other location convenient to the subject by a trained study nurse or will be self-administered by the subject and/or caregiver.

Specific procedures for each visit are listed in the Study Flow Chart in Section 3.

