# 12.4.2 Outpatient Administration (Day 4 to Day 336)

From Day 4 through Day 336 daily doses of APL-2 will be administered off-site by a trained nurse or self-administered by the subject and/or caregiver, at the subject's home, workplace, or other location convenient to the subject with the exception of clinical site visit days (see above). Home nursing is an optional service and is not required if subject can properly self-administer APL-2. Home nursing may be started/re-started if subject requires additional training on self-administration.

Subject, caregiver, and/or nurse is to report adverse events and concomitant medications to the clinical site.

Note: Study Procedures for Visit 15 (Day 336) may be different for subjects that elect to enter the Part B Long-Term Extension Phase. These subjects may initiate a different dose regimen of APL-2 and will be dispensed drug for home administration. If a subject is to enter the Part B Long-Term Extension Phase and it is confirmed that the subject will initiate the APL-2 dose regimen intended for use during the Long-Term Extension Phase (APL-2 1,080 mg twice weekly), the subject should be instructed to skip their Core Study Phase dose the day before Visit 15. Subjects that will not initiate a new dose at Visit 15 should take their regular Part A Core Study Phase daily dose through Visit 15.

Section 17.3 provides details on the Long-Term Extension Phase.

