#### Part B: Long-Term Extension Phase:

Following Visit 15 (Week 48), subjects who elect to continue in the Part B Long-Term Extension Phase will return to the site at 12-week intervals indefinitely until the subject discontinues or the development program is terminated.

Specific procedures for each visit are listed in the Study Flow Chart for the Long-Term Extension Phase in Table 2 in Section 3.3.2.

At Visit 15 (Week 48), subjects electing to enter the Part B Long-Term Extension Phase will begin an APL-2 dose regimen of APL-2 1,080 mg twice weekly (with potential to escalate to APL-2 1,080 mg every 3 days). When switching from the Part A Core Study Phase formulation and dose of APL-2 (270 mg/d or 360 mg/d) to the formulation and dose intended for use in the Long-Term Extension Phase (APL-2 1,080 mg twice weekly), subjects should return to the site for APL-2 administration training and to conduct Dose Transition Visits 1, 2 and 4 weeks after the new dose is initiated and perform the procedures outlined in Appendix Section 8.1.

Subjects who plan on continuing in the Part B Long-Term Extension Phase should be instructed to skip their daily Part A Core Study Phase Dose the day prior to Visit 15 (i.e., the subject should not self-administer APL-2 on Day 335).

**Note:** The first dose of APL-2 1,080 mg should be administered at the Visit 15 (Day 336), with Dose Transition Visits at Week 49, Week 50, and Week 52. Some subjects may enter the Part B Long-Term Extension Phase prior to the availability of the sorbitol formulation. These subjects should continue on their Part A Core Study Phase dose into the Part B Long-Term Extension Phase. These subjects will transition to the Long-Term Extension Phase dose at the next scheduled visit at which the sorbitol formulation and dose is available, and should schedule Visits T1, T2, and T3 1, 2 and 4 weeks following the visit at which the sorbitol dose is initiated. These subjects should be instructed to skip their Part A dose the day before the visit at which the APL-2 1,080 mg twice weekly dose regimen is scheduled to be initiated.

Subjects who discontinue treatment early should complete one Early Termination Follow-up Visit (ETFU) 6 weeks after discontinuation of treatment, and one Early Termination (ET) Exit Visit 6 weeks after the ETFU as outlined in Appendix 8.1.

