#### Part B

Part B baseline for this study will be derived as the last measure prior to the first 1080 mg APL-2 dose.

Unless indicated otherwise Part B change from baseline (Part B CFB) will be calculated as follows for after Part B Study Day 1:

Part B CFB = Visit Result – Part B Baseline Result

Percent change from baseline (Part B PCFB) will be calculated as follows:

Part B PCFB (%) = 100\*(Visit Result – Part B Baseline Result)/ (Part B Baseline Result) Where Part B Baseline is the last assessment prior to the first 1080 mg APL-2 dose on Part B Study Day 1.

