# 5.4.2 Pharmacokinetic Parameters

For both Part A and Part B, the following PK parameter for APL-2 will be derived using actual sample times:

Ctrough,max Maximal observed serum concentration. As later PK samples are collected pre-dose this is termed maximal trough concentration.

 $C_{trough,max}$  will be calculated for both 270 mg and 360 mg where subjects receive both doses during Part A, and for Part B

The derived PK parameter will be listed by cohort and dose (for  $C_{trough,max}$ ). The PK parameter will also be summarized using descriptive statistics. Geometric mean and CV will be included in the descriptive statistics.

Apellis Pharmaceuticals, Inc.
Protocol: APL2-CP-AIHA-208
Part B Long Term Extension Statistical Analysis Plan

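### Part B PK rules do not follow the dosing interval: a 1-day cut-off kept from daily dosing can drop a stopping subject's trough, and Visit 15 pools 48-h with 24-h samples

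*SAP*

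**What the plan says.** **Exclusion rule.** SAP 5.4 (27 Apr 2020, used for the Part A interim analysis) and Part B SAP 5.4.1 (08 Nov 2022) carry the same sentence: "If a subject discontinues APL-2 dosing, then concentrations from samples collected more than 1 day after the last dose will be excluded from calculations". Neither gives a different limit for Part B.

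**Dosing.** In Part A, "Subjects will receive daily SC doses of APL-2 on Days 1 through Day 336" (Protocol 12.4). On entering Part B, subjects "will begin an APL-2 dose regimen of APL-2 1,080 mg twice weekly (with potential to escalate to APL-2 1,080 mg every 3 days" (Part B SAP 3.3).

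**Skipped dose.** Protocol 12.4.2 says that, where a subject is confirmed to start the new regimen at Visit 15, "the subject should be instructed to skip their Core Study Phase dose the day before Visit 15". Part B SAP 3.3 names the day: "the subject should not self-administer APL-2 on Day 335". Subjects who do not yet change regimen take their usual dose, and omit one the day before the later visit at which they switch.

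**PK summaries.** Samples after Day 1 are pre-dose (Protocol 13.2.1). Part A concentrations are summarised by visit, by randomized dose and by current dose, with no split by time since the last dose. The only PK parameter is Ctrough,max: "As later PK samples are collected pre-dose this is termed maximal trough concentration" (Part B SAP 5.4.2).

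**Related definitions.** Part B SAP 4.2.1 ends Part B on the date of the last dose. Part B SAP 5.1.6.1 takes one dose off the expected Part A count for subjects who rolled over, because of the skip.

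**The concern.** A cut-off after the last dose should remove washout samples and keep the end-of-interval trough. One day does that under daily dosing. Under twice-weekly or every-3-days dosing it also removes the trough itself. A subject who stops at a Part B visit loses a sample that would be kept, at the same time since dosing, if the subject continued.

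The Visit 15 issue is separate. The row mixes two sample types: about 48 h after the last dose for those switching there, and about 24 h for the rest. The SAP adjusts compliance for the skipped dose but has no matching PK rule. Treatment of a 48-h sample is also uneven: it is excluded if the subject has stopped and kept if the subject rolls over.

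PK is a stated objective, and by-visit concentrations are one of its main outputs. A reader of the table would take the Visit 15 row as a daily trough.

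**Working it through.** The documents give no PK figure on this point, so there is nothing to reproduce.

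**Inputs**
- Part A interval: 1 day.
- Part B interval: 7/2 = 3.5 days on average (twice weekly) or 3 days. The compliance formulas in Part B SAP 5.1.6.1 use the same intervals.
- A PK sample is scheduled at Visit 15 (Protocol Table 1).
- Half-life: about 7.5 days in monkeys (Protocol 5.2). The text reviewed gives no human value, so I assume 5 to 10 days.

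**Cut-off**
1. A regular Part B trough lies 3.5 × 24 = 84 h or 3 × 24 = 72 h after the previous dose. Both exceed 24 h, so the rule always excludes a stopping subject's trough.
2. The cut-off covers 1/3.5 = 29% or 1/3 = 33% of the interval.
3. The next scheduled visit is 6 weeks after stopping (Part B SAP 3.3). The sample at risk is therefore the one taken at the visit where dosing stops: at most one per such subject.
4. Part B SAP 4.2.1 closes Part B on the last dose date. Changing 5.4.1 alone would still leave that sample outside Part B.

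**Visit 15 timing**
- Switching at Visit 15: last dose Day 334, so (336 − 334) × 24 = 48 h.
- Not switching there: last dose Day 335, so (336 − 335) × 24 = 24 h.

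**Size of the skip effect**

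With exponential decline, k = ln 2 / half-life, and the 48-h value divided by the 24-h trough is exp(−k × 1 day).

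To allow for subcutaneous absorption, take a single-dose curve c(t) = ka/(ka − k) × [exp(−kt) − exp(−ka·t)]. Sum it over doses on Days 1 to 334 to get C48 on Day 336. Then C24 = C48 + c(1), and the ratio is C48/C24. The absorption rates ka are assumptions.

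| Half-life | Exponential | ka 2.0/day | ka 1.0/day | ka 0.5/day | ka 0.3/day |
|---|---|---|---|---|---|
| 5 days | −12.9% | −11.2% | −8.2% | −5.1% | −3.4% |
| 7.5 days | −8.8% | −7.6% | −5.6% | −3.5% | −2.3% |
| 10 days | −6.7% | −5.8% | −4.2% | −2.6% | −1.7% |

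**Effect on the row mean.** If a share f of the row switched at Visit 15 and subjects are otherwise alike, the mean moves by f times the drop. At 7.5 days with exponential decline: one in six gives 8.8/6 = −1.5%, half gives −4.4%, all gives −8.8%. The documents do not state f.

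**Which rows are mixed.** The rows for all subjects randomized to a dose pool the two sample types whatever current dose is coded. The rows restricted to subjects on their randomized dose pool them if the pre-dose sample is coded to the daily dose.

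**The case against.** The exclusion applies only on discontinuation, and with the next visit 6 weeks away it mainly removes washout samples, which is its evident purpose. The loss needs a subject to be sampled but not dosed at the stopping visit. This stands, and it limits the first part to an edge case.

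The skip is already visible: the SAP lists actual sample times with deviation from nominal, and plots each subject's concentrations with a dosing overlay. That is true, but no summary rule uses the information.

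Several stronger readings are tempting, and the documents do not support them.
- *All rollovers are affected at Visit 15.* The SAP sentence that those continuing "should be instructed to skip their daily Part A Core Study Phase Dose the day prior to Visit 15" could suggest this. Its own note and Protocol 12.4.2 confine the Visit 15 skip to subjects who start 1,080 mg there.
- *The Part A to Part B exposure comparison is biased.* Neither SAP plans such a PK contrast. Illustrative figures are also fragile. With a 7.5-day half-life and a bolus model, the trough change from 360 mg/d to 1,080 mg twice weekly is −24% and reads −17% against the 48-h value; from 270 mg/d it is +1% and reads +11%. At the 280 mg nominal dose allowed in Protocol 7.2.1, the latter pair becomes −2% and +7%, so even the sign of the underlying change is not settled.
- *Ctrough,max is distorted.* It is a maximum, so one low Visit 15 value will seldom move it.
- *Part B PD results are biased.* The rule "Part B baseline for this study will be derived as the last measure prior to the first 1080 mg APL-2 dose" does make the PD baseline a post-skip value. But no concentration-response relation is given, so no PD bias has been quantified, and taking the last pre-switch value as baseline is ordinary practice.

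**Conclusion.** Both parts hold, with modest consequences. The 1-day limit does not fit Part B and can exclude one valid trough per subject who stops undosed at a visit. The Visit 15 row mixes about-48-h with 24-h samples, because subjects who start 1,080 mg there have omitted the Day 335 dose. Those who switch later give the same kind of sample at their switch visit.

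Affected values are about 7 to 13% lower under simple exponential decline, and about 2 to 11% lower once slow absorption is allowed for. Both ranges rest on an assumed half-life of 5 to 10 days, centred on a monkey figure.

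The effect is confined to by-visit descriptive concentration summaries. The trial is a descriptive pilot, and this does not touch the primary safety endpoint or haemoglobin. It calls for a clarification of PK handling. Protocol 17.3 and its Part B schedule were not in the text reviewed, so Visit 15 sampling is taken from the Part A flow chart.

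**What to change.** In the Part B SAP:
1. In 5.4.1, exclude samples taken more than one dosing interval after the last dose, using the SAP's own intervals (1 day daily, 3.5 days twice weekly, 3 days every 3 days) plus a stated timing tolerance. The tolerance matters: a fixed twice-weekly calendar alternates 3- and 4-day gaps, averaging 3.5.
2. In 4.2.1, align the end of Part B for PK with that cut-off, so that a retained trough still counts as Part B.
3. Flag samples taken after the instructed skipped dose, at Visit 15 or the later switch visit, and show them in a separate row from the 24-h troughs.

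The cost is SAP wording and a time-since-last-dose flag, which the planned timing listing already supports. The downside is a smaller n in the Visit 15 24-h row. No change to the dosing instruction is proposed.

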# 5.4.2 Pharmacokinetic Parameters

For both Part A and Part B, the following PK parameter for APL-2 will be derived using actual sample times:

Ctrough,max Maximal observed serum concentration. As later PK samples are collected pre-dose this is termed maximal trough concentration.

 $C_{trough,max}$  will be calculated for both 270 mg and 360 mg where subjects receive both doses during Part A, and for Part B

The derived PK parameter will be listed by cohort and dose (for  $C_{trough,max}$ ). The PK parameter will also be summarized using descriptive statistics. Geometric mean and CV will be included in the descriptive statistics.

Apellis Pharmaceuticals, Inc.
Protocol: APL2-CP-AIHA-208
Part B Long Term Extension Statistical Analysis Plan

# 6. TESTING/QUALITY CONTROL PLAN AND SOFTWARE/SYSTEM

Version 1.0

All statistical programs, excluding PK analysis programs, will be written in SAS® version 9.4. Statistical programs will be tested and reviewed for Quality Control (QC) by a second programmer/biostatistician not involved in the programming as per DPC's standard operating procedure (SOP). In addition, DPC's SOP will be followed to ensure that the information is complete, consistent, and accurately reflects the data stored in the database. Further all TLFs will undergo a QC process by an independent biostatistician/programmer to ensure that the information is complete, consistent, and accurately reflects the data.

# 6.1 **Programming Specifications for TLFs**

Appendix 8.1 provides a list of all the TLFs that are planned to be produced.

# 6.2 Formatting Conventions

The following formatting conventions will be used to output TLFs:

- TLFs are outputted by SAS Output Delivery System (ODS) into Rich Text Files (RTF) format.
- Tables and Listings will include borders around all headings and data cells.
- Output will be in landscape orientation with margins of 0.75 inches on bottom, left, and top, and 3/8 inch for right.
- The default font to be in tables/listings/figures will be Courier New.
- Preferred and minimum font size:

Portion of Output	Preferred	Minimum
Page Header	9 pt	8 pt
Title	9 pt	8 pt
Column header	9 pt	8 pt
Cells	9 pt	8 pt
Footnote	9 pt	8 pt
Page Footer	9 pt	8 pt

• Data will be centered within columns when the maximum length of the data being displayed is less than or equal to the maximum width of the

column heading. When the maximum length of the data being displayed exceeds the maximum width of the column heading, the data will be left-justified.

- Column headings should be in initial capital characters. For numeric variables, include "unit" in the column heading when appropriate.
- In figures, axes will be labeled appropriately.

### 6.3 Standard Text Conventions

### 6.3.1 Header

All output (table, listing, or figure) will have the following header, as applicable:

```
Apellis Pharmaceuticals, Inc.
Protocol: APL2-CP-AIHA-208
Part B Long-Term Extension Study Report
```

Page xx of XX

All output will have the date and time (date and time output was generated) and internal page number in the header. Tables/Listings/Figures should be internally paginated (i.e., page numbers should appear sequentially within each output).

# 6.3.2 Title

At least three (3) lines, in general, will be reserved for the entire title.

- The first line is for the table/listing/figure number;
- The second line is for the actual title; and
- The third line is reserved for the analysis set descriptor.

All titles will be centered, as shown in the following example:

Table 14.3.1.1 Topline Summary of Adverse Events Safety Set

#### 6.3.3 Footnotes

Unless otherwise specified, footnotes will appear on all pages within the tables and listings as follows:

- Footnotes will be in the format of "NOTE: then the footnotes", as shown in the following example:
- NOTE: SD = Standard Deviation.
- Each line of a complete footnote should end with a period.
- When an abbreviation (e.g. AE, SAE, etc.) appears first time in the whole set of TLFs for a study, a footnote should be provided at least once; and it is up to the study statistician, to decide whether there is a need to repeat the same footnote for the rest of TLFs.
- A footnote serves as a brief explanation/clarification /definition /concept of a flag symbol or a character, an abbreviation, a terminology, etc., that appears in or relates directly to the displayed content of a table/listing/figure.
- All footnotes will be at the lowest line of the page immediately above the footer. The footer will be directly on the line below the last footnote.
- For Tables, first footnote will provide source listings and/or analysis datasets names for cross-referencing.

